Extensive research in animal models has shown a benefit to using intravenous (IV) vitamin C in sepsis.^{4,5} It is a cofactor for multiple enzymatic functions.⁶ In addition, one study in particular found that critically ill patients, including those with sepsis have significantly lower levels of circulating vitamin C during their acute illness than their healthy counterparts. Furthermore, the investigators found critically ill patients who were administered an infusion of vitamin C every six hours maintained normal plasma levels for the largest amount of time.⁶ One study showed that critically ill patients required up to 3 grams per day of vitamin C just to return their plasma concentrations to normal baseline levels.⁷ Additional research indicates that critically ill patients are often thiamine-deficient which is frequently missed and not treated by their clinicians.^{8,9}

Marik et al. published a novel study implicating the use of IV vitamin C, vitamin B₁, and hydrocortisone resulted in a significantly lower mortality rate for their septic patients. His team explored the utility of these medications as compared to historical controls of their previously treated septic patients.¹⁰ This study, while novel and inspiring, was designed with the acceptance of multiple confounders and potential for bias including the retrospective nature, the lack of randomization, and the lack of blinding. We propose investigating the use of IV vitamins B₁ and C in a randomized, prospective trial, eliminating the potential for selection bias.

Hypotheses

[figure not shown]
1. Primary Hypothesis: Septic patients in the ICU who receive IV vitamins B₁ and C will demonstrate a decreased mortality rate compared to septic patients who do not receive IV vitamins B₁ and C.
2. Secondary Hypotheses: Patients receiving IV vitamins B₁ and C
 - a. will have shorter hospital length of stays (HLOS)
 - b. will have shorter ICU length of stays (ICU LOS)
 - c. will demonstrate a lower 30-day readmission rate
 - d. will have fewer ventilator days
 - e. will have fewer hours on vasopressors
 - f. in addition to IV hydrocortisone for refractory septic shock will have a more profound reduction in mortality when as compared to those receiving IV vitamins B₁ and C alone

g. who also record to higher Sequential Organ Failure Assessment (SOFA) scores will have a more significant reduction in mortality than patients who record lower SOFA scores

Objectives

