Prior to the recruitment process the pharmacy will enter numbers 1-120 in ascending order into a randomizing website. This randomly assigned each number to either placebo or intervention. Prior to recruitment, kits in blocks of 10, containing either the placebo or unmixed forms of vitamin B₁ and C are made and placed in identical packages labeled with their corresponding number. These numbers will be assigned in ascending order corresponding to the order in which they are consented. Once ordered by the providers the pharmacy will open the identical kits and, if it is the intervention, mix the vitamin B₁ and C for IV administration. This process will ensure the study coordinators, healthcare providers, and the patients remain blinded. Vitamins B₁ and C will be ordered for all patients in Epic, giving the impression that all of those

enrolled are in the intervention group. However half the kits will contain the intervention and half will contain the placebo. This is being done due to logistical issues with preparing and storing the vitamin B₁ and C. Having premade kits allows the pharmacy to more easily prepare and distribute the vitamin B₁ and C. These also need to be refrigerated and given limited space kits will be made in blocks of 10 to limit crucial storage space the pharmacy needs for other medications.

We plan to enroll 120 patients; 60 in the control arm and 60 in the intervention arm. Our current mortality rate is 35% at Saint Francis Hospital and Medical Center for patients with severe sepsis and septic shock. We expect our mortality rate to decrease to 30% with this intervention. We believe this is a reasonable expectation given that Marik et al. demonstrated that his intervention group's mortality rate dropped from 40.4% to 8.5% after a similar intervention.¹⁰ In order to demonstrate this difference, 120 patients are needed according to our power calculation.

Informed Consent/Ethical Issues

We anticipate a full board IRB approval, as this is a prospective study involving vitamins B₁ and C as the intervention. Appropriate patients will be approached and consented (often via proxy consent) by members of the research team. Patients will then be randomized by computer to receive vitamin C and vitamin B₁, or normal saline (control). The treating physicians, the research team, and the patients will all be blinded. The pharmacist mixing the drugs will be the only non-blinded team member.

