The study personnel will report adverse events as soon as they become aware of them and within 24 hours of them being informed. All adverse events or unanticipated problems will be reported to the IRB. If the adverse event is thought to be related to the intervention, the medication will be stopped and the patient will be withdrawn from the study. They will be monitored closely for resolution of the adverse event. In order to ensure that the patient receives the ideal treatment for their adverse reaction and their newly-discovered allergy is documented appropriately, the research staff will un-blind the ICU staff and themselves. This will be accomplished by keeping duplicate sealed randomization envelopes. In the case of an adverse event, the research staff will open this additional envelope and inform the treating physicians.

Side Effects

Possible side effects for patients receiving IV vitamin C include diarrhea, nausea, vomiting, heartburn, headache, insomnia, and nephrolithiasis. Possible side effects for patients receiving IV vitamin B₁ include nausea, hives, wheezing, or angioedema. In the event of these reactions, the patients will be treated immediately for their allergic reaction by the primary team and will be withdrawn from the trial as previously mentioned.

Study Withdrawal

All patients who have a serious adverse event thought to be directly related to the intervention will be withdrawn from the study. The patient or their consenting proxy may revoke consent and withdraw from the study at any point as participation is completely voluntary.

Statistical Issues

The intervention arm (vitamin B₁ and C) and the control arm (sodium chloride 0.9%) will be compared statistically for demographics and patient characteristics; including age, gender, comorbidities, need for operative intervention, enteral nutrition, and Body Mass Index (BMI). Outcomes between these two groups will also be compared including hours of vasopressor use, ventilator days, HLOS, ICU LOS, comorbidities, renal function measured by patients' GFR and creatinine levels, procalcitonin levels, SOFA scores, discharge destination, readmission rates, and mortality rates. We will do a subgroup analysis of patients with septic shock as compared to those with severe sepsis. We will also do a subgroup analysis of the patients who receive hydrocortisone as opposed to those who do not.

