Fisher's exact test will be used to compare gender, operative intervention, rate of mortality and the 30-day readmission rate. Average BMI and average age will be evaluated via student's t-

test. Median number of ventilator days, average hours of vasopressor use, median daily SOFA scores, average procalcitonin levels, average creatinine levels, median GFR, median ICU LOS and median HLOS will all be compared via Mann-Whitney U test. A contingency table will be used to analyze the different types of enteral nutrition and patients' discharge destination. A multivariate regression analysis will be conducted to analyze patients' comorbidities.

Duration of Review

We will start recruiting patients on September 10, 2018. We expect recruitment and data collection to take 12 months. Data analysis and completion of a manuscript is expected to take another 12 months.

All data will be kept on a password-protected and encrypted computer located behind two locked doors. We will retain all data for three years after the completion of the study. Following this, all data will be deleted from the hard drive where they will be kept.

Publication Plan

We plan to write and submit a manuscript for publication in a peer-reviewed journal.

References

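### Secondary hypothesis 2g (larger mortality reduction at higher SOFA) has no planned analysis, and the septic shock versus severe sepsis subgroup analysis has no stated method or interaction test

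*Combined protocol and SAP*

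**What the plan says.** Under Hypotheses, secondary hypothesis g states that treated patients with higher SOFA "scores will have a more significant reduction in mortality than patients who record lower SOFA scores". That is a statement about effect modification. It gives no SOFA cut-off and no time at which the score is taken.

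Under Statistical Issues, SOFA is listed among the outcomes to be compared between arms, and "median daily SOFA scores" are assigned to the Mann-Whitney U test. No analysis uses SOFA as a modifier of the treatment effect.

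The same section says "We will do a subgroup analysis of patients with septic shock as compared to those with severe sepsis". It names no test, effect measure or interaction term for this. Fisher's exact test is the only test named for mortality. The one regression mentioned is for comorbidities, and no treatment-by-covariate term is described.

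The sample size paragraph, under Enrollment/Randomization, gives the planning figures: a local control mortality of 35%, a target for the treated arm ("We expect our mortality rate to decrease to 30% with this intervention"), and a total of 120 split equally between the arms.

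**The concern.** Whether a treatment works better in one kind of patient than in another is a question about the difference between two effects. It is answered by estimating that difference with its uncertainty. Fisher's test on mortality by arm, whether in all patients or within a subgroup, does not estimate it.

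Two things follow. First, a stated secondary hypothesis has no analysis attached, so whatever is eventually reported for 2g will have been chosen after the fact, including the cut-off and the day of the score. Second, the named tools leave an analyst of the shock subgroups with a p-value in each. If one is below 0.05 and the other is not, it is easy to report that the vitamins work only in the first group. That pattern can arise when the true effect is identical in both, because each subgroup is small.

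The time point also matters. SOFA is recorded daily and treated as an outcome. If 2g were analysed with scores taken after dosing began, patients would be grouped by something the treatment may have changed.

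**Working it through.** **1. The plan's own figure.** The plan attributes 120 patients to a power calculation for 35% versus 30%: "In order to demonstrate this difference, 120 patients are needed according to our power calculation". Alpha, sidedness and power are not given. Assuming two-sided 0.05 and 80% power, with average rate 0.325:

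n per arm = [1.960 × √(2 × 0.325 × 0.675) + 0.842 × √(0.35 × 0.65 + 0.30 × 0.70)]² / 0.05² ≈ 1,377, or 2,754 in total.

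The figure of 120 does not reproduce. That is a separate and larger problem; it matters here because it means that subgroup effects will be very imprecise.

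**2. Inputs for the subgroup check.** Control mortality of 35%, planned 30% and 60 per arm come from the sample size paragraph. So does the optimistic pair, 40.4% and 8.5%, from the earlier before-after study: "intervention group's mortality rate dropped from 40.4% to 8.5% after a similar intervention". The 20% and 15% rates are illustrative. Subgroup sizes are not in the documents. I assume 30 per arm in each of two subgroups, with 40/20 and 45/15 per arm as the range, and equal numbers by arm within each subgroup.

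**3. Chance that exactly one subgroup is significant when the true effect is the same in both.** Let p be the exact probability that a two-sided Fisher test at 0.05 rejects with 30 per arm, found by enumerating both binomials. Then P(exactly one) = 2p(1 − p). For 35% versus 30%: 2 × 0.0387 × 0.9613 = 0.074.

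| True mortality, both subgroups | p (30 per arm) | Exactly one significant, 30/30 | Range over 30/30, 40/20, 45/15 |
|---|---|---|---|
| 35% v 35% | 2.6% | 5.0% | 4.7% to 5.2% |
| 35% v 30% (planned) | 3.9% | 7.4% | 7.2% to 7.6% |
| 35% v 20% | 17.6% | 29.0% | 29% to 31% |
| 35% v 15% | 33.0% | 44.2% | 44% to 50% |
| 40.4% v 8.5% | 77.8% | 34.6% | 35% to 60% |

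**4. The same, given a significant overall Fisher test at 60 per arm.** Exact enumeration over all four cells, 30/30 split: exactly one subgroup is significant in about 54% of such trials at 35% versus 30%, 60% at 35% versus 20%, 61% at 35% versus 15%, and 35% at 40.4% versus 8.5%. At 35% versus 30% the overall test is itself significant in only about 6% of trials.

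**5. Interaction test on the same data.** A Wald test on the difference in log odds ratios (0.5 added to each cell) falsely signals a difference in 4.7% of trials with no effect, 4.5% at 35% versus 30%, and about 2% to 5% across all scenarios and splits.

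**6. What the interaction test can detect.** At 35% versus 30%, 30 per arm per subgroup:

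- Variance of the interaction log odds ratio = 2/(30 × 0.35 × 0.65) + 2/(30 × 0.30 × 0.70) = 0.293 + 0.317 = 0.610, so SE = 0.78.
- For 80% power, the ratio of odds ratios must be exp(2.802 × 0.781) ≈ 8.9, or its inverse, about 0.11.
- If mortality falls from 35% to 25% in one subgroup and not at all in the other, the log ratio is −0.480 and the SE 0.786, so power is about 9%.

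**The case against.** A reader might infer three stronger things. None is supported as it stands.

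- **That a false subgroup-only finding is likely.** At the plan's own effect it is not: about 7% per split, or 6.7% if only significance in the direction of benefit counts (2.5% with no effect). Rates near one half need a true reduction of about 20 points or more. The much larger reduction in the before-after study is cited only to support the expected 30%. What stands is the conditional figure: if the trial is positive overall, about half or more of such trials would show exactly one significant subgroup in three of the four effect scenarios.
- **That the plan prescribes separate tests and a comparison of their p-values.** It does not say so. It speaks of one group compared with the other and names no method, and the sentence on Fisher's test is not tied to subgroups. The accurate criticism is that no method or interaction test is specified.
- **That the protocol claims a different effect by shock status, or will group patients by post-dose SOFA.** Neither is stated. The hypothesised modifiers are hydrocortisone (2f) and SOFA (2g); shock status is only an announced subgroup. For SOFA, the supportable point is that no time point is given.

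The other fair objection is that an interaction test has so little power here that 2g will stay unanswered in practice. That is correct. The value of the test is that it blocks unsupported claims and gives an honest interval; it will not confirm a real difference of plausible size. These are also secondary, exploratory questions that leave the primary comparison untouched.

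**Conclusion.** The point holds in limited form. Hypothesis 2g asserts effect modification and has no analysis. The shock subgroup analysis has no stated method. Nothing named in the plan can test whether effects differ.

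The false-pattern rate is modest at the planned effect (about 7% against 4.5% for an interaction test) and large only if the true effect is much bigger (29% at 35% versus 20%, 44% at 35% versus 15%) or once the overall result is significant (about 54% at 35% versus 30%). These figures rest on assumed subgroup sizes, balance by arm within subgroups, an identical true effect in both, and two-sided 0.05. The gap in the plan does not depend on them. The change should be made, but it does not bear on the primary result.

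**What to change.** Add to Statistical Issues:

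- For shock status: a logistic model for mortality with arm, shock status at randomisation, and arm × shock.
- For hypothesis 2g: a logistic model for mortality with arm, SOFA as a continuous score (last value before the first study dose), and arm × SOFA.
- Report each interaction odds ratio with its 95% CI, and claim a differential effect only from the interaction. Show within-subgroup mortality by arm descriptively, without subgroup p-values.
- Label both analyses exploratory, and state that power to detect a true interaction with 120 patients is very low (80% power needs a ratio of odds ratios of about 9 under the 30/30 assumption).
- Reword 2g as a larger reduction in mortality, since a more significant one could be read as a comparison of p-values.

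The cost is a few sentences and two models. No extra patients or procedures should be needed, but the team should confirm that shock status at randomisation and a pre-dose SOFA score are recorded for everyone, since the documents mention only daily scores. The drawback is that the intervals will be wide, and the report must say so.

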Data will be kept on an encrypted, password-protected computer behind two locked doors. Data will be managed by the investigators who will each have their own login.

Study Workflow

Patients admitted to the ICU who have severe sepsis or septic shock will be identified by the nursing staff, PAs, or physicians caring for them. These patients' consenting party will be approached within 24 hours of their presentation to the ED in an attempt to obtain informed consent. Following consent, the pharmacy will be notified of the study patient, randomization will occur, and the mixed medications (control or intervention) will be delivered to the patient's bedside in the ICU. Consented patients will receive 1.5g of vitamin C in 100mL of 0.9% sodium chloride (normal saline) every six hours for four days or until discharge from the ICU, whichever happens first (seventeen dose maximum). In addition, they will receive 200 mg IV vitamin B₁ every 12 hours in 100 mL of normal saline for four days or until ICU discharge (whichever happens first, nine dose maximum). Patients in the control arm will receive the 100 mL of 0.9% sodium chloride every six hours and 100 mL of 0.9% sodium chloride every 12 hours to act as placebos for the vitamin C and B₁ respectively. Doses up to 200 mg/kg/day were found to be safe in humans in one study.⁶ Several studies have been conducted in human subjects using IV vitamin B₁ and C, often at higher doses than proposed here, and have not seen serious side effects.^{10,12-14}

Some patients may receive hydrocortisone IV for refractory septic shock outside of this study protocol. This will be at the discretion of the treating physician and will not be included in the randomized and blinded intervention. Hydrocortisone has been shown in some studies to help

in patients with refractory septic shock.^{15,16} However, it is not uniformly employed. Patients receiving hydrocortisone will undergo a subgroup analysis to better elucidate the synergistic effects of hydrocortisone with vitamins B₁ and C.

After discharge, patients will be followed for 30 days to track hospital readmissions.

Reporting of Adverse Events

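### The 30-day readmission comparison (hypothesis 2c) has no rule for death, so a treatment that lowers mortality can look worse on it and a harmful one can look better

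*Combined protocol and SAP*

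**What the plan says.** Under Hypotheses, the primary hypothesis is that patients given the vitamins "will demonstrate a decreased mortality rate compared to septic patients who do not receive IV vitamins". Item 2c of the secondary hypotheses is that they "will demonstrate a lower 30-day readmission rate". Study Workflow describes the data collection: "After discharge, patients will be followed for 30 days to track hospital readmissions". Statistical Issues names the test: "Fisher's exact test will be used to compare gender, operative intervention, rate of mortality and the 30-day readmission rate".

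Nothing further is specified for this endpoint. The plan does not say whether the denominator is all randomised patients or those discharged alive. It does not say how a death in hospital, or a death in the 30 days after discharge, is classified. It names no composite with death and no competing-risk method. Mortality is compared as a separate outcome, without a time point.

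The planning figures for mortality are under Enrollment/Randomization: "Our current mortality rate is 35% at Saint Francis Hospital and Medical Center for patients with severe sepsis and septic shock", and "We expect our mortality rate to decrease to 30% with this intervention". In support, the protocol cites a before-after study in which the "mortality rate dropped from 40.4% to 8.5% after a similar intervention".

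**The concern.** Death competes with readmission: a patient who dies in hospital can never be readmitted, and one who dies soon after discharge may have no chance to be. The primary hypothesis is that treatment changes the death rate, so the arms are expected to differ in how many patients are at risk of readmission.

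Neither available denominator avoids this. With all randomised patients, a death in hospital adds to the denominator but never to the numerator, so it is scored like a good outcome. With patients discharged alive, the groups compared have been selected by the primary outcome, and randomisation no longer protects the comparison. At stake is the reading of 2c: a higher readmission rate in the treated arm could reflect lives saved, and a lower one could reflect deaths.

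**Working it through.** The plan gives no figure for readmission, so there is none to reproduce. Its only calculated figure, the sample size, concerns mortality and does not bear on this point.

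**Inputs.** From the protocol: mortality of 35% (control) and 30% (intervention), 60 patients per arm, and 40.4% and 8.5% in the cited study. Assumed, because the documents give no values: the stated mortality occurs before discharge; r is the readmission risk of a patient discharged alive; rx is the readmission risk of the extra survivors that treatment produces.

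**1. Denominator: all randomised patients.** Rate = (1 − mortality) × r. With equal r in both arms, r cancels from the ratio.
- Planned mortality: 0.70/0.65 = 1.08. At r = 20%: 0.65 × 0.20 = 13.0% vs 0.70 × 0.20 = 14.0%. For r from 10% to 40%, the difference is 0.5 to 2.0 points.
- To break even, r in the treated arm must fall by 1 − 0.65/0.70 = 7.1% (relative).
- Cited study's mortality: 0.915/0.596 = 1.54. At r = 20%: 11.9% vs 18.3%.
- Harm, with treated mortality assumed to be 40%: 0.60/0.65 = 0.92, so the harmful arm looks better.

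**2. Denominator: patients discharged alive.** Control rate = r. Treated rate = (control survivors × r + extra survivors × rx) / treated survivors. With r = 20%:
- Planned mortality, rx = 20%: no difference.
- Planned mortality, rx = 10%: (0.65 × 0.20 + 0.05 × 0.10)/0.70 = 19.3%, which favours treatment.
- Planned mortality, rx = 30%: 0.145/0.70 = 20.7%. With rx = 40%: 0.150/0.70 = 21.4%.
- Cited mortality, rx = 30%: (0.596 × 0.20 + 0.319 × 0.30)/0.915 = 23.5%. With rx = 40%: 27.0%.

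**3. Deaths after discharge, if entered as not readmitted.** Suppose 10% of control and 5% of treated patients die after discharge before any readmission, and r = 20% in the rest. The rates are 0.90 × 0.20 = 18.0% vs 0.95 × 0.20 = 19.0%.

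**4. Size against the noise.** Exact enumeration of Fisher's test was run with 60 per arm, all randomised patients as denominator, equal r and an assumed two-sided 5% level. The chance that treatment looks significantly worse is 1.9% (r = 20%) to 2.3% (r = 30%) at 35% vs 30% mortality. At 35% vs 8.5% it is 7.7% to 12.3%.

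**5. Death or readmission, all randomised patients.** Rate = mortality + readmissions per randomised patient.
- Planned mortality, r = 20%: 0.35 + 0.13 = 48.0% vs 0.30 + 0.14 = 44.0%, or 44.5% to 45.0% if rx is 30% to 40%.
- Cited mortality: 0.404 + 0.119 = 52.3% vs 0.085 + 0.183 = 26.8%, or 30.0% to 33.2% if rx is 30% to 40%.
- Share of deaths among control events at planned mortality: 0.35/0.48 = 73%.

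In these scenarios the composite moves with the mortality effect.

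**The case against.** The strongest reply is that this is a gap in wording with little numerical effect. Follow-up begins after discharge, so patients discharged alive are the more natural denominator. On that reading nothing is distorted if the extra survivors have the same readmission risk, and treatment looks better if theirs is lower. At the planned mortality the all-randomised distortion is 13% vs 14%, or 7.8 vs 8.4 patients out of 60, about half a patient. The large figures need the mortality of a retrospective study that the protocol itself describes as open to confounding and does not adopt as its planning effect. Readmission is one of seven secondary hypotheses, and mortality is reported for the same arms. A composite made up mostly of deaths largely repeats the primary outcome.

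Much of this stands. It limits the size and rules out calling the endpoint useless. It does not remove the problem. The discharged-alive reading is still conditioned on the primary outcome, and its neutrality rests on an untestable assumption about the extra survivors. Reporting mortality alongside may not help fully: with no time point for mortality, and follow-up described only in terms of readmissions, a death at home might appear in neither endpoint.

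A reader might also infer that the plan codes a death after discharge as not readmitted. No text says so. It is what a plain yes/no table would do by default, and the plan is silent.

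**Conclusion.** The point holds as a cheap improvement to a secondary endpoint. As planned, a treatment that lowers mortality can look worse on 2c, and a harmful one can look better.

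It would be too strong to say that a life-saving treatment must look worse. That follows mechanically only with all randomised patients as denominator and equal risk in survivors. Among patients discharged alive, the direction depends on the extra survivors. Nor do rates of 23% to 27% vs 20% apply at this trial's planning figures; they need the cited study's mortality. At 35% vs 30% the corresponding figures are 20.7% to 21.4% vs 20%.

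At the planned effect the distortion is therefore about 0.5 to 2 points with all randomised patients, and 0.7 to 1.4 points among those discharged alive if the extra survivors' risk is 30% to 40%. Both are small against the noise of 60 per arm. The distortion becomes material only with a large mortality effect. These sizes rest on assumed readmission risks and on treating the stated mortality as in-hospital, which the protocol does not say.

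**What to change.** - Record vital status, with date of death, at the 30-day post-discharge follow-up already planned.
- Make the inferential analysis supporting 2c a Fisher's exact test of death or readmission up to 30 days after hospital discharge, in all randomised patients, with death in hospital counted as an event.
- Keep the readmission rate among patients discharged alive. Label it as conditional on survival, and show it beside the numbers of in-hospital and post-discharge deaths in each arm.

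The cost is one reworded secondary analysis and one extra field at an existing contact. The downside is that the composite is largely deaths (about 73% of control events at 35% mortality and an assumed 20% readmission risk) and overlaps the primary outcome. Its components must therefore be reported separately, and it should not be presented as independent confirmation of a mortality result.

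### Mortality, the primary hypothesis, is tested only by an unadjusted Fisher's exact test; a prespecified covariate-adjusted analysis, or Boschloo's test, would use the same 120 patients somewhat better at little cost

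*Combined protocol and SAP*

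**What the plan says.** The Hypotheses section makes mortality primary: treated patients "will demonstrate a decreased mortality rate compared to septic patients who do not receive IV vitamins". Under Statistical Issues the only test named for it is Fisher's "exact test will be used to compare gender, operative intervention, rate of mortality and the 30-day readmission rate".

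The same section contains one model: "A multivariate regression analysis will be conducted to analyze" the patients' comorbidities. This names a class of variable, but no outcome and no treatment term. Comorbidities are listed there both as a patient characteristic and among the outcomes, so their role in the model is unclear.

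The section already plans to use three likely prognostic variables:
- Age is compared between arms.
- Septic shock versus severe sepsis defines a subgroup.
- SOFA is listed among the outcomes and again, in the list of tests, as "median daily SOFA scores". No pre-dose SOFA value is singled out.

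Enrollment/Randomization sets 60 patients per arm and a current mortality of 35%, and adds: "We expect our mortality rate to decrease to 30% with this intervention". In support it cites a before-after study in which the "mortality rate dropped from 40.4% to 8.5% after a similar intervention".

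**The concern.** Fisher's test conditions on the total number of deaths. At this sample size its attainable p-values are coarse, so the real false-positive rate sits well below the nominal one, and power is lost with it. Leaving out baseline prognostic variables can lose more, because differences in risk between patients stay in the noise. The trial is small, so neither loss is easily spared, and recovering part of it needs no extra patients.

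There is a second, smaller benefit. The one regression that is planned could be read as a mortality model, a model of something else, or a comparison of comorbidities. Writing out the mortality model in advance removes that choice after the data are seen.

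**Working it through.** **Inputs from the documents.** 60 per arm; 35% versus 30%; 40.4% versus 8.5% (all Enrollment/Randomization).

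**Assumptions.** Two-sided alpha 0.05; illustrative effects of 35% versus 20% and 35% versus 15%; the covariate strengths given below.

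**1. The plan's own figure.** The plan says 120 patients are needed to show 35% versus 30%. At two-sided 0.05 and 80% power (also assumed), with mean rate 0.325:

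n per arm = [1.960·√(2·0.325·0.675) + 0.842·√(0.35·0.65 + 0.30·0.70)]² / 0.05² = (1.298 + 0.557)² / 0.0025 ≈ 1,377.

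The stated 120 in total is not reproduced. This is a separate and larger problem. It matters here because it limits what any choice of test can achieve.

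**2. Unadjusted tests.** All 61 × 61 possible tables were enumerated. Power = Σ Bin(x; 60, p₁)·Bin(y; 60, p₂) over the tables with p ≤ 0.05; size is the same sum with p₁ = p₂. Boschloo's test rejects when Fisher's p is at most 0.0665, the largest cut-off that keeps maximum size at or below 0.05.

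| | Fisher | Boschloo | mid-p | chi-square |
|---|---|---|---|---|
| Size, 35% both arms | 3.05% | 4.47% | 4.76% | 5.04% |
| Size, 30% both arms | 3.08% | 4.13% | 4.83% | 5.25% |
| Maximum size | 3.5% | 4.9% | 5.5% | 5.5% |
| Power, 35% v 30% (plan) | 6.0% | 7.9% | 8.6% | 9.2% |
| Power, 40.4% v 8.5% (cited) | 98.3% | 98.9% | 99.0% | 99.1% |
| Power, 35% v 20% (assumed) | 37.5% | 42.2% | 45.0% | 46.5% |
| Power, 35% v 15% (assumed) | 65.2% | 70.0% | 72.2% | 73.5% |

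**3. Adjusted logistic regression, Wald test on arm.** 20,000 trials were simulated per scenario (Monte Carlo standard error at most 0.35 points). Covariates: SOFA, age, and shock at 50% prevalence with latent correlation 0.5 with SOFA. Assumed odds ratios for SOFA per SD, age per SD and shock: weak 1.5/1.2/1.3, middle 2.0/1.3/1.5, strong 2.7/1.5/2.0.

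| | weak | middle | strong |
|---|---|---|---|
| Power, 35% v 30% | 9.4% | 9.6% | 9.8% |
| Power, 40.4% v 8.5% | 98.7% | 98.9% | 99.2% |
| Power, 35% v 20% | 45.9% | 49.8% | 53.6% |
| Power, 35% v 15% | 73.8% | 76.4% | 80.7% |

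Size was 4.8-5.1% throughout. A different model (one baseline covariate with assumed AUC 0.63 to 0.81, likelihood-ratio test, 10,000 trials) gave 47.5% to 57.6% at 35% versus 20%. The direction is the same, and the upper end clearly depends on the assumed covariate strength.

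**4. Gains over Fisher.**
- 35% v 30%: from 7.9 − 6.0 = 1.9 (Boschloo) to 9.8 − 6.0 = 3.8 points (strong covariates).
- 40.4% v 8.5%: from 98.7 − 98.3 = 0.4 to 99.2 − 98.3 = 0.9 points.
- 35% v 20%: from 42.2 − 37.5 = 4.7 to 53.6 − 37.5 = 16.1 points.

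Adjustment beyond chi-square, at 35% v 20%, runs from 45.9 − 46.5 = −0.6 to 53.6 − 46.5 = 7.1 points.

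**5. Limits on the model.** Expected deaths are 60·0.35 + 60·0.30 = 39 at the plan's rates, and 60·0.35 + 60·0.20 = 33 at the assumed 20%. That supports about three covariates. At 8.5% the intervention arm expects 60·0.085 = 5.1 deaths and has none with probability (1 − 0.085)⁶⁰ ≈ 0.5%. The Wald test fails in that case.

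**The case against.** The strongest reply is that an unadjusted exact test is a normal, clearly stated choice for a binary outcome in a randomised trial. That stands: the point concerns efficiency.

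The gain is also small at both effects the documents give, and at 35% versus 30% it is partly bought with alpha. Moving from Fisher to chi-square adds 9.2 − 6.0 = 3.2 points of power, while size rises by about 2.0 to 2.2 points. That stands too. The larger gains appear only at effects and covariate strengths that had to be assumed. The simulation also favours adjustment, since the fitted model is the true one and no SOFA score is missing. At the cited effect, weak-covariate adjustment (98.7%) falls slightly below chi-square (99.1%).

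A reader might infer more than the text supports:
- *That Fisher's test biases the comparison.* It does not; it is valid here.
- *That the regression names no covariates at all.* It names comorbidities as a class.
- *That SOFA enters the analysis only as daily scores.* The list of outcomes has SOFA scores without that qualifier. What is missing is a fixed pre-dose value.
- *That the unstated alpha, sidedness and mortality time point prove the analysis wrong.* They are missing detail. They must be filled in before any mortality model can be written, but the point does not rest on them. Follow-up is stated for readmission only: "After discharge, patients will be followed for 30 days to track hospital readmissions".

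**Conclusion.** The point holds as a cheap improvement to the primary mortality analysis, for the sponsor to consider. Fisher's test uses about 3.1% of an assumed 5% alpha at the mortality rates the plan expects, and it ignores baseline information the trial already means to use. Replacing it gains about 2 to 4 points of power at the plan's own effect, 1 point or less at the cited one, and about 5 to 16 points at an assumed 35% versus 20%. With weak covariates, nearly all of the benefit comes from leaving Fisher and adjustment adds essentially nothing.

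The unadjusted figures are exact, given two-sided 0.05 and 60 per arm. The adjusted figures also rest on the assumed odds ratios. It would be wrong to read the change as a rescue of the design: at 35% versus 30%, power stays at about 8-10% whichever replacement is chosen.

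**What to change.** State alpha, sidedness and one mortality time point, and add wording such as:

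> The primary analysis is a logistic regression of mortality at the stated time point on treatment arm, adjusted for the last SOFA score before the first dose, age, and septic shock versus severe sepsis at randomisation. The arm term is tested by the Wald test at two-sided 0.05. The odds ratio and standardised risk difference are reported with 95% confidence intervals.

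Also state:
- **No adjustment for post-randomisation variables.** Hydrocortisone use after randomisation is the obvious case: "Some patients may receive hydrocortisone IV for refractory septic shock outside of this study protocol".
- **Missing SOFA.** Impute without reference to arm or outcome, for example with the overall mean.
- **Fallback.** If an arm has no deaths or the model does not converge, use Boschloo's test or Firth-penalised logistic regression, whichever is named in advance.
- **Sensitivity analysis.** Keep an unadjusted test.
- **Comorbidity regression.** Keep it as a separate secondary analysis and name its outcome. It is the plan's only named method for comorbidities and should not be dropped.

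If an unadjusted primary test is preferred, Boschloo's test keeps exact size control and is more powerful than Fisher's. Mid-p and chi-square give slightly more power, with size up to 5.5%.

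The cost is analysis wording and one fixed pre-dose SOFA value per patient, which would also serve the secondary hypothesis on SOFA. Two limits should be accepted openly. The model should hold about three covariates. The normal-theory interval for the standardised risk difference is slightly too narrow at this size (its test ran at 5.4-5.7% in simulation), so the formal test should stay with the Wald statistic. Randomisation, treatment and sample size are unchanged.
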